#### **PROSPER (Parent Trial)**

#### 1.0 Objectives

1.1 Primary Objective: Investigate the impact of our sleep enhancement intervention, which entails a wearable digital vital sign monitoring device, on variation in the quality of life of acute care cancer patients

#### 1.2 Secondary Objectives:

- a. Assess the impact of our sleep enhancement intervention on acute care utilization e.g. length of stay, 30-day readmissions
- b. Assess the implementation and feasibility of wearable digital vital signs capture in an inpatient oncologic setting using validated instruments such as system usability scale (SUS) and Weiner implementation outcomes (AIM, FIM, IAM).
- c. Assess the impact, via validated survey instruments, of our sleep enhancement intervention on patient mood, patient activation and satisfaction with inpatient stay experience.

#### 2.0 Background/Rationale

Post hospitalization syndrome refers to a generalized increased risk for a range of adverse health related events following an acute hospitalization. The mechanism is thought to be driven by allostatic and physiologic stress acquired during the hospitalization. Sleep disruptions, deconditioning from acute illness, loss of personal autonomy, pain, and disruption of normal circadian rhythms are prominent examples. Numerous reports have documented the prevalence and risk of these perturbations. The clinical impact of post-hospitalization syndrome is also being increasingly recognized. This includes but is not limited to immune dysfunction, coagulopathy, impaired physical coordination and poor wound healing. According to estimates, up to 20% of Medicare beneficiaries (approx. 2.6 million seniors) are readmitted within 30 days for reasons unrelated to the diagnosis that prompted the index admission. As a result, post-hospitalization syndrome has become the impetus for numerous quality improvement (QI) initiatives that promote successful recovery. A prominent example involves a multi-level QI project implemented at Ochsner clinic that bundled reduced nighttime noise, passive vital monitoring, delayed morning phlebotomy and use of red-enriched lighting after sunset. This program was associated with reduced length of stay (LOS), improved readmission rates and enhanced sleep quality across a sample of 3425 consecutive medical-surgical patients. However, it is unclear whether and to what extent these findings are generalizable to a population of acute care cancer patients. Phase I of the PROSPER protocol involved the use of various standard of care methods to minimize sleep interruptions during the hours or 10pm to 6am including, noise monitoring and reduction strategies, minimizing bedtime medication administration, delayed early morning phlebotomy, and use of red-light instead of white light when provider-patient interactions were necessary. These interventions were bundled into a "clustered care approach" along with eliminating nocturnal vital sign check when possible. Clustered care has been shown to improve sleep quality, improve

patient satisfaction and clinical outcomes. One concern with clustered care regarding avoiding intermittent nocturnal vital sign checks is that these sleep interruptions are justified by the need to anticipate and prevent clinical deterioration. In this proposal we aim to use an FDA-approved digital vital sign motioning device (ViSi Mobile, Sotera Wireless, San Diego CA) to replace manual nurse bedtime vital sign check allowing for vital sign evaluation at the clinically appropriate cadence without compromising sleep quality.

This FDA approved digital wearable technology that continuously monitors vital signs has previously been demonstrated in peer-reviewed studies to improve outcome measures such as decreased need to call rapid response teams, ICU transfer, length of stay, and 30-day mortality. To our knowledge, the effects of substituting digital motoring for manual nocturnal vital sign checks, and the effects of reducing / eliminating sleep interruptions on sleep quality and quantity in an acute oncologic setting has not been previously reported. **Our aim is to investigate the impact of the Phase II of our "PROSPER" bundle with the addition of digital passive vital sign monitoring to replace routine nocturnal vital sign checks on sleep hygiene (quantity and quality), clinical outcomes (LOS, readmission) and patient-centered outcomes (patient experience and satisfaction) in an acute oncologic patient population.** 

#### **Hypothesis**

We hypothesize that the implementation of our wearable technology intervention will result in a reduced LOS, lower 30-day readmission rates, and improved patient recovery (sleep quality and quantity), and enhanced subjective measures of patient engagement (PAM-13), satisfaction (HCAHPS) and well-being (EQ-5D-5L).

#### 3.0 Research Plan

#### 3.1 Study Population

This study will include consented consecutive patients who are admitted to the medical-surgical floor at MD Anderson Cancer Center (Texas Medical Center location only) for the conditions and/or surgical procedures outlined below.

#### 3.2 Inclusion Criteria

Adult patients (> 18 years of age), English-speaking, able to complete consent and survey materials. Patients must be admitted to the hospital for at least 3 nights. Patients using pharmacological sleeping aides will be included in the study, as this will help us understand if the intervention also helps patients with pre-exisitng sleep disturbances.

#### 3.3 Exclusion Criteria

Vulnerable populations (pregnancy, incarcerated, history of delirium, suicidal ideation, ischemic stroke with measurable neurologic deficit, cerebral palsy, seizures).Patients concurrently enrolled in contact isolation with SARS-CoV2 will be excluded. Lastly, hospice or hospice-bound patients will also be excluded. Any patient can remove themselves from the study at any point.

#### Table 1: Study participants

Participating Surgical Services	Participating Medical Services
Colorectal Surgery	Hospitalist service

#### 3.4 Study Design

This is a pragmatic, quasi-experimental study wherein patients admitted for any of the aforementioned conditions will be allocated into treatment (ViSi mobile plus PROSPER) and control (PROSPER only) based on non-critical care bed availability on a floor unit. Specifically, for patients on colorectal service admitted to P10 floor, one side ("unit A") will be designated as an intervention arm while the other ("unit B") will serve as a control arm. For patients admitted to Hospitalist Medicine service; patients on " unit G21" will be designated as the intervention arm, and patients admitted to "unit G22" as the control arm. Our pseudorandomization scheme is based on the naturally occurring random variation in bed assignment by availability across both the intervention and control units on a given floor, or floors at the time of patient enrollment. Since bed designation is made by hospital admissions based on availability, it is independent of the care delivery processes across the study floors / units. Our approach is intended to reduce the

burden on frontline staff, i.e., changing existing workflows to randomize patients and track allocation in a database. It also serves to reinforce the embedded intent of our QI work. Participants, family members and clinicians will not be blinded to the intervention, and given our pragmatic design, we will not attempt to control patients' communication or information-seeking behaviors beyond the pseudo-randomization described above. The intervention wing will employ the following initiatives to improve the sleep quality, level of engagement, and overall care journey of patients.

1. Passive digital monitoring of vital signs – Blood pressure, heart rate, respiratory rate, oxygen saturation, and temperature – will be wirelessly and passively collected using a U.S. Food and Drug Administration-approved wireless technology, which is worn on the wrist and chest (ViSiMobile, Sotera, San Diego, Calif), and recorded data will be sent directly to the electronic medical record (Epic Systems Corporation, Verona,Wis) at protocolized set intervals. Abnormal vitals will trigger a nursing alert via text message or page. If an in-person assessment is warranted, handheld red-spectrum lighting will be used by nursing staff as an alternative to the standard overhead white lighting.

An intervention checklist will be created to ensure consistent adherence and documentation. Monthly feedback sessions will be held with the respective care teams to solicit frontline feedback with respect to implementation issues. Patients in the control arm will receive routine care per hospital routine.

#### 3.5 Recruitment

Potential participants admitted to participating floors in the study will be identified in the EMR. Research coordinators will approach patients to participate in the study within 1-2 days of admission. The recruitment process will be documented and attested by the Investigators and their delegates.

#### 3.6 Informed Consent

Informed Consent from eligible patients will be obtained following the Clinical Research Informed Consent SOP 4.0.

#### 3.7 Patient Allocation to study groups

There is generally one patient per room and patient assignment to a room is largely driven by unit census (i.e., bed availability) as well as other clinical factors: e.g., need for an isolation room, nursing availability. All of these factors vary independently of the preferences of the patient or research team, reducing the risk for systematic bias. The unit of randomization is by pod on a floor. Research coordinators as part of the "on-boarding process" will also provide culturally competent instructions and in-person teaching for device use.

#### 3.8 Data collection

This will entail a blend of Epic medical record abstraction and primary data collection using validated surveys. Example of variables to be exstracted from the medical record include patient demographics (e.g., age, sex, race), primary diagnosis (cancer type), body mass index (BMI), timing of AM phlebotomy, comorbid conditions (used to compute Charlson co-morbidity index), length of stay, and 30-day readmission. To reduce survey burden for patients and ensure parity in scope of responses across the 2 groups, the majority of questionnaires will be distributed at two time points - at admission and within 24 hours of the date of discharge. All validated surveys will be administered via the hospital-owned iPad device, via text message or email, or recorded manually. A password-protected database will be used to collate the clinical and outcomes data collected. Lastly, all patients will receive a phone call 24 hours after discharge to ensure all questions are answered and follow-up care has been arranged.

2022-0190 v.23Mar2023 Page **4** of **18** 

The digital device is worn on the wrist, like a watch, and provides continuous vital sign monitoring using a three-lead system that included electrocardiography (ECG), pulse oximetry, continuous noninvasive blood pressure, mean arterial pressure, temperature, respiratory rate, heart rate, and pulse rate. Patients will be able to view their vital signs on the wrist-worn device's display screen.

Pre-programmed alarm parameters for abnormal vital signs will be established by the research team in close collaboration with the clinical and nursing leadership of each participating service (Table 1). Nurses will be alerted to abnormal vital signs via secure machine to nurse messaging via a Sotera app on the iPhone device that is carried by each nurse. This workflow is consistent with published literature. Continuous monitoring data from all patients wearing the ViSi Mobile monitor will be recorded directly into the electronic medical record at intervals determined by the clinical team. (EPIC, Epic Systems, Verona WI) and will also be temporarily stored in an on-premise server. The ViSi Mobile data will be periodically accessed and downloaded into a virtual private cloud operated by Sotera Wireless on Amazon Web Services. This data does not include protected healthcare information and is deidentified. It includes all vital signs, device data, user interactions, and full waveform data, including high frequency ECG, PPG, and

accelerometer data. This information will be attributed to a unique patient via time stamp and the ViSi Mobile device ID of the wrist monitor. The device ID must be recorded for all consenting patients in the EMR. Sotera Wireless research staff will access the cloud data and apply signal processing and machine learning algorithms to quantify metrics and events from the continuous monitoring data during sleep. MD Anderson staff will annotate events, collect patient reported outcome responses (Table 2 and 3). Also, in addition to vitals and alarms the MD Anderson EMR will be configured to record VISI Mobile Device ID for each patient placed on continuous monitoring. The device ID will allow patient data in the Sotera cloud server to be linked to patient data in the EMR by MD Anderson staff. Sotera will have access to designated MD Anderson research staff and clinicians to collaborate on the development of novel metrics, graphic reports, and explore how patient care would benefit from clinically meaningful alerts triggered by the new information. Access to MD Anderson research staff & clinicians will include a minimum of 4 hours of clinical collaboration and consultation on a quarterly (3-month) basis throughout the duration of the proposal. MD Anderson staff will have the ability to correlate this new information with EQ-5D scores, PAM-13 scores, HADS scores, Richard Campbell Questionnaire responses, and implementation outcome surveys.

#### 3.9 Outcomes

Patient-Centered Outcomes (Primary): The present study will be powered to the EQ-5D measure at discharge, our primary outcome, which allows us to discern variations in self-reported quality-of-life over the course of the inpatient care episode that is attributable to our intervention (Table 2)

Primary Outcome	Instrument	Duration	Analysis level	Assessment Calendar
Quality of Life	EQ-5D-5L	2-5 min	Patient	Admit, discharge +/- 1
				day
Secondary Outcome	Instrument	Duration	Analysis level	Assessment Calendar
Patient Engagement	PAM-13	3 min	Patient	Admit, discharge +/- 1
				day
Patient Mood	Hospital Anxiety &	2-5 min	Patient	Admit, discharge +/- 1
	Depression Survey (HADS)			day

#### **Table 2: Patient Reported Outcomes**

Patient Satisfaction	1. HCAHPS	7 mins	Floor unit	4x a year (rolling)
	2. Net Promoter Score	2 mins	Patient	Discharge +/- 1 day
Sleep Perception	Richard Campbell Sleep	1 min	Patient	Admit, discharge +/- 1
	Questionnaire (Daily)			day

PAM: Patient Activation Measure; EQ-5D-5L: EuroQol – 5 dimension – 5 level; HADS: Hospital Anxiety and Depression Scale; HCAHPS – Hospital Consumer Assessment of Healthcare Providers and Systems

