#### **Table 3: Implementation Outcomes**

- c. Secondary patient-reported outcomes: Validated surveys that capture patient mood (HADS), engagement with care (PAM), and satisfaction with inpatient stay (HCAHPS, Net promoter score), outlined in Table 2 as well, will also be administered to intervention and control patients according through a pre-specified schedule.
- d. Sleep interruption and relationship to patient outcomes: Sleep interruptions between the control and intervention arms will be collected electronically from the hospital Electronic Medical Record

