#### 3.11 Sample size justification

Preliminary calculations, based on an estimated conservative change of 10% from baselines scores in QOL, as measured by the EQ-5D instrument total score (with a baseline of mean of 13 units and standard deviation of 5 units). We expect to detect a significant change with at least 80% power using 250 patients per treatment arm. To account for increased estimation variance due to propensity score-based reweighting (and a small rate of drop-out after enrollment), we plan to enroll 350 patients per treatment arm to ensure a reasonable expectation of significance.

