#### 4.3 Research Plan

- a. *Study Population:* In order to participate in the sub-study, participants must be enrolled in the PROSPER trial. We plan to enroll 100 participants from the parent trial in this pilot study, 50 participants from each arm of the parent trial. The inclusion and exclusion criteria for the sub-study are the same as the parent trial.
- b. *Inclusion criteria:* Adult patients (> 18 years of age), English-speaking and able to complete consent and survey materials are eligible to participate. Potential participants must be admitted to the hospital for an anticipated minimum of 3 nights.
- c. *Exclusion criteria:* Vulnerable populations (pregnant, incarcerated, history of delirium, suicidal ideation, ischemic stroke with measurable neurologic deficit, cerebral palsy, seizures), primary brain tumor/metastases patients) are not eligible. Patients concurrently enrolled in contact isolation with SARS-CoV2 will be excluded. Lastly, hospice or hospice-bound patients will also be excluded. Any patient can remove themselves from the study at any point.

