#### **Richards-Campbell Sleep Questionnaire**

You are now ready to begin to answer the questions. Place your "X" anywhere on the answer line that you feel best describes your sleep last night.

1. 1	dy sleep last night was:	
	Deep Sleep	Light Sleep

2. Last night, the first time I got to sleep, I:

Fell	Just Never
Asleep	Could Fall
Almost	Asleep
Immediately	

3. Last night I was:

Awake	
Very	Awake All
Little	Night Long

4. Last night, when I woke up or was awakened, I:

Got Back	Couldn't
To Sleep	Get Back To
Immediately	Sleep

5. I would describe my sleep last night as:

A Good	A Bad
Night's	Night's
Sleep	Sleep

nsidered

2022-0190 v.23Mar2023 Page 14 of 18

Hospital Anxiety and Depression Scale (HADS) Instructions: Doctors are aware that emotions play an important part in most illnesses. If your doctor knows about these feelings he or she will be able to help you more. This questionnaire is designed to help your doctor know how you feel. Read each item and circle the reply which comes closest to how you have been feeling in the past week. Don't take too long over your replies: your immediate reaction to each item will probably be more accurate than a long thought out response.

I feel tense or 'wound up':	A	I feel as if I am slowed down:	D
Most of the time	3	Nearly all of the time	3
A lot of the time	2	Very often	2
Time to time, occasionally	1	Sometimes	1
Not at all	0	Not at all	0
I still enjoy the things I used to enjoy:	D	I get a sort of frightened feeling like 'butterflies in the stomach':	A
Definitely as much	0	Not at all	0
Not quite so much	1	Occasionally	1
Only a little	2	Quite often	2
Not at all	3	Very often	3
get a sort of frightened feeling like something awful is about to happen:	A	I have lost interest in my appearance:	D
Very definitely and guite badly	3	Definitely	3
res, but not too badly	2	I don't take as much care as I should	2
A little, but it doesn't worry me	1	I may not take guite as much care	1
Not at all	0	I take just as much care as ever	0
can laugh and see the funny side of things:	D	I feel restless as if I have to be on the	A
As much as I always could	0	Very much indeed	3
Not quite so much now	1	Quite a lot	2
Definitely not so much now	2	Not very much	1
Not at all	3	Not at all	0
Worrying thoughts go through my mind:	Α	I look forward with enjoyment to things:	D
A great deal of the time	3	A much as I ever did	0
A lot of the time	2	Rather less than I used to	1
From time to time but not too often	1	Definitely less than I used to	3

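### The one-night sleep form is labelled daily but scheduled at two points, and its discharge window lets it rate a night at home (minor)

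*Combined protocol and SAP*

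**What the plan says.** **Schedule.** Table 2 (section 3.9) lists the Richards-Campbell form under Sleep Perception. Its instrument entry includes "Questionnaire (Daily" (bracket closed after that word). The calendar entry in the same row is admission and discharge, plus or minus one day. Section 3.8 says that "the majority of questionnaires will be distributed at two time points - at admission and within 24 hours of the date of discharge", and names no exceptions. No daily schedule for this form appears elsewhere in the parent trial.

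**Delivery.** Under section 3.8 surveys may be "administered via the hospital-owned iPad device, via text message or email, or recorded manually", so a patient can answer after leaving the hospital.

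**Recall period.** The form in the Appendix tells the patient to mark "anywhere on the answer line that you feel best describes your sleep last night". It covers one night and no more.

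**Role.** The Hypothesis section expects "improved patient recovery (sleep quality and quantity"; the closing bracket follows. Table 2 places the form among the secondary outcomes. The list in section 3.9(c) does not name it: "Validated surveys that capture patient mood (HADS), engagement with care (PAM), and satisfaction with inpatient stay (HCAHPS, Net promoter score", again with the bracket closing after. Nor do the secondary objectives in section 1.2 name sleep perception. Section 3.9(d) separately collects sleep interruptions in both arms from the medical record.

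**Numbers.** Section 3.11: "we plan to enroll 350 patients per treatment arm". Section 4.3 (sub-study): "We plan to enroll 100 participants from the parent trial in this pilot study".

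**The concern.** There are two linked problems in one table row.

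First, a coordinator or analyst cannot tell from the plan whether to expect two forms per patient or one for each day in hospital. That affects data collection and the form of the analysis.

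Second, a discharge window of one day either side suits instruments with a long recall period. HADS in the Appendix asks about the past week, and the PROMIS forms in the sub-study use seven days. For those, a one-day slip changes a small part of the period rated. For a form that asks about a single night, it replaces the whole period. A sleep form answered the day after discharge describes a night when neither the intervention nor the control unit was caring for the patient. No rule says which night counts, and no field for its date is described, so such forms could not be reliably identified afterwards.

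At stake is the interpretation of the discharge sleep rating, in a trial whose intervention is meant to reduce night-time disturbance in hospital.

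**Working it through.** **1. Which night each form rates.** Call the admission day 0 and let the stay be L nights, so that discharge is on day L. A form about the previous night, completed on day d, rates night d, the night ending that morning.

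| Form completed | Night rated | Example, L = 3 (minimum stay, section 3.2) |
|---|---|---|
| Day before discharge | L − 1 | night 2, in hospital |
| Day of discharge | L | night 3, in hospital |
| Day after discharge | after night L | post-discharge night |

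The last row holds for every L. The Table 2 window permits it, the section 3.8 timing permits it, and remote delivery makes it practicable.

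**2. The admission end.** Section 3.5 has patients approached one to two days after admission. A form on day 0 rates a night before admission; on day 1 or day 2 it rates hospital night 1 or 2. For L = 3, an admission form on day 2 and a discharge form on the day before discharge both rate night 2. Recording the date of the night rated would show this as well.

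**3. Who depends on this form.** Planned enrolment is 2 × 350 = 700 (section 3.11). PROMIS Sleep Disturbance and actigraphy are confined to the 100 sub-study patients (section 4.3). That leaves 700 − 100 = 600, and 600/700 = 86%, for whom this form is the only patient-rated sleep measure listed.

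**4. Size of the dilution, two-point reading.** Let p be the share of discharge forms that rate a post-discharge night, taken as equal in both arms. Let c be the fraction of the in-hospital effect that persists on those nights. The observed contrast, as a fraction of the in-hospital contrast, is

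(1 − p) + p·c = 1 − p(1 − c).

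Neither p nor c is in the documents. With assumed values:

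| p | c = 0 | c = 0.5 | c = 1 |
|---|---|---|---|
| 5% | 95% | 97.5% | 100% |
| 10% | 90% | 95% | 100% |
| 30% | 70% | 85% | 100% |

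Dilution therefore needs both late forms and incomplete carry-over. The plan states no figure for this outcome, so there is none to reproduce.

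**The case against.** **The label may not conflict with the calendar.** *Daily* stands in the instrument column and can describe the one-night recall, while the calendar column gives the schedule. That is a fair reading, and a reader who infers a flat contradiction goes beyond the text. What stands is the ambiguity: section 3.8 speaks only of most questionnaires, so a daily form is not ruled out. Neither reading removes the post-discharge night.

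**Carry-over is plausible.** The Background rests on hospital stress persisting after discharge, so a zero effect on home nights is an assumption. A reader might infer that discarding post-discharge forms is always the better choice. That holds only when c is near zero. If information is taken as proportional to the number of forms times the squared contrast, keeping them is worth (1 − p(1 − c))² against 1 − p for leaving them out. The two are equal at c = 1 − (1 − √(1 − p))/p, about 0.49 at p = 5% or 10% and 0.46 at p = 30%. Above that, keeping them is more efficient. Leaving patients out by the timing of their form, which is fixed after allocation, also sits badly with the intent-to-treat framework of section 3.10. This objection stands against simple exclusion. It does not stand against closing the window in advance and knowing which night was rated.

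**The form is not the trial's only sleep outcome.** This is correct: sleep interruptions come from the medical record under section 3.9(d). They are not patients' ratings of their sleep, so the narrower statement in step 3 holds.

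**The window is the same in both arms.** This is true, and under equal shares the result is dilution and not a spurious difference. Equal shares are still an assumption. If late completion differed by arm, any difference between home and hospital sleep would enter the contrast, and the documents give no basis for sizing it.

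**Conclusion.** The point holds, as a minor one. The Sleep Perception row has to be reconciled, because its label and calendar allow two schedules and section 3.8 does not choose between them. Following the stated window can also produce a discharge rating of a night outside both arms' units. That follows from the recall period and the window together and needs no assumption.

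The size does rest on assumptions. With equal shares in the arms and no carry-over, the contrast is diluted by exactly the share of post-discharge forms, which the documents do not give. With carry-over the loss is smaller, and with full carry-over it is nil.

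A reader might infer that the trial's sleep conclusion is unreliable or that its power is at risk. The documents do not support that. The form is a secondary outcome by virtue of Table 2 alone, the share of late forms may be small, and the EQ-5D primary outcome and the section 3.11 sample size do not depend on it.

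**What to change.** 1. **Table 2, Sleep Perception row.** State whether *Daily* means frequency or recall, and make the calendar agree. Add a sentence to section 3.8 saying whether this form is an exception to the two time points.
2. **Window, for this form only.** Close the discharge window on the day of discharge, so that the form rates an in-hospital night. The other instruments can keep their window.
3. **Date field.** Record the date of the night rated on every form, at admission and at discharge.
4. **Analysis, section 3.10.** Make in-hospital nights the main arm comparison. Keep any post-discharge forms that still arrive for a sensitivity analysis, so that the carry-over question is examined and not assumed away.

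**Cost.** One table row, one sentence in section 3.8, one date field and a short addition to section 3.10. The drawback is that some late forms become missing and then fall under the missing-at-random assumption and the sensitivity analysis already planned there. If daily collection is what is intended, the number of forms grows with length of stay, at about one minute each by Table 2. That must be weighed against section 3.8's aim of limiting survey burden.
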